2.6. Why to carry out this cRCT in Ghana?

Recently, Ghana has come under scrutiny for human rights violations against people with psychosocial disabilities, as denounced in several reports by local and international organizations [9, 21, 59]. According to these reports, in psychiatric facilities, Ghanaians with psychosocial disabilities experience poor conditions of the physical infrastructure, insufficient food, and overcrowding. Many residents are forced to live in these institutions against their will and without any possibility to challenge their situation. Verbal and physical abuse are commonly used when persons try to escape, complain about pain, and fail to take medication or follow hospital rules. Unmodified electroconvulsive therapy (i.e., without anesthesia) is used, and people are often isolated in seclusion rooms for up to three days, although such practices constitute ill-treatment and may amount to torture according to the UN special rapporteur on torture. Many people residing in psychiatric facilities spend their days outside the hospital buildings, under the hot sun, with little or no shade and without being engaged in any activity. The situation is no better in the general community, where Ghanaians with a psychosocial disability are frequently believed to be “possessed by evil spirits” or “bewitched” and thus are deemed dangerous [175-177]. As a result, families often send them to traditional or faith-based healing institutions (the so called “prayer camps”) where they are arbitrarily detained for as long as payment to the institution is sustained [9, 21, 59]. Ghanaians with psychosocial disabilities in prayer camps are often chained to trees, frequently in the baking sun, and forced to fast for weeks as part of the “healing process,” while being denied access to medications [9, 21, 59]. Some prayer camps also employ whipping and scarification as a form of treatment [9, 21, 59].

In 2012, to eliminate the widespread human rights violations against people with psychosocial disabilities in mental health facilities and the community, Ghana ratified the UN CRPD and enacted a Mental Health Act [60]. The Act created a Mental Health Authority (Ministry of Health), for which the initial priority was the promotion of the rights of Ghanaians with psychosocial disabilities. To achieve this objective, in February 2019, the Ministry of Health and several Ghanaian organizations of people with psychosocial disabilities launched the “QualityRights in Mental health, Ghana” [178], a project which aims to undertake a country-wide implementation of the WHO QualityRights initiative. As part of this project, they are planning to use the WHO QualityRights online modules to train different stakeholders, including mental health providers, but they would like to evaluate the efficacy of the training before scaling it up at the national level. The cRCT I propose is aligned with this necessity, and the expressed strong policy goals of the government of Ghana.

3. Research Design and Method

3.1 Methodology

- **Aim: To conduct a cRCT in Ghana to determine the efficacy of the QualityRights training compared with a placebo intervention in improving the knowledge about human rights and the attitudes of mental health professionals towards people with psychosocial disabilities and their role as right-holders.**
Secondarily, we want also to determine
 - **if the QualityRights training, compared with a placebo intervention, is effective in changing the practices and experiences related to substitute-decision making and coercion among mental health providers.**

3.1.1 Design

3.1.1.1. Research protocol

The study proposed is part of the project funded by the European Commission (EIDHR 2018-400431) “Empowering persons with psychosocial disabilities to fight for their rights: An implementation of the CRPD and QualityRights principles in Ghana, Lebanon, and Armenia.” The University of Cagliari, in Italy, is the project leader for this project. In Ghana, the project is implemented by the Mental Health Authority - Ministry of Health, the Mental Health Society of Ghana (an organization of persons with psychosocial disabilities), and MindFreedom Ghana (an organization working to promote human rights in mental health). The WHO (Headquarter and Europe Offices) and the Office of the United Nations High Commissioner for Human rights are official partners of the project and are guiding the implementation of the CRPD and QualityRights principles in Ghana. These organizations have been (and will be) involved in all the phases of the study proposed. Approval of the research protocol will be sought by Ethics committees at the Ghana Health Service and Columbia University.

3.1.1.2. Study setting

The trial will be conducted in Ghana. In this country, mental health services are mainly provided in urban areas, either within the three large psychiatric hospitals or in smaller psychiatric units in the three teaching hospitals and five regional hospitals [164]. For this study, participants will be recruited from mental health professionals working in three psychiatric hospitals: Accra, Pantang, and Ankaful. Accra Psychiatric Hospital has a bed capacity of 600 and is located in the Greater Accra Region. Pantang Psychiatric Hospital is a 500-bed hospital also located in the Greater Accra region. Ankaful Psychiatric Hospital is a 350-bed hospital located in the Central Region of Ghana. All three psychiatric hospitals also have outpatient units. They are located in the southern part of the country and serve a population of approximately 25 million persons [179]. Appendix 3 provides further information about the study setting.

3.1.1.3. Study Design

The study will be a cluster Randomized Controlled Trial (cRCT) with hospital units as the clusters to be randomized to the intervention and control arms. Participants will be selected in three steps. First, 28 units (12 from Accra, 12 from Pantang, and 4 from Ankaful) will be randomly selected among the 44 units (19 from Accra, 19 from Pantang, and 6 from Ankaful) of the three psychiatric hospitals for participation in the study. Second, within each of the three psychiatric hospitals, units will be randomized to the intervention and control arms using a 1:1 allocation ratio. The allocation of units will be carried out by an independent researcher based at the University of Cagliari using a computerized randomization sequence. Unit randomization will be completed before the participants are recruited. The local trial coordinator will obtain a letter of permission signed by the Mental Health Authority (Ministry of Health) Chief Executive to access the register of mental health professionals employed in the three psychiatric

hospitals. In each randomized unit, a random sample of potentially eligible mental health professionals identified from the registers will be invited via email or telephone by trained research assistants to be screened for eligibility. Persons who give informed consent to the research assistants to be screened for eligibility will be recruited after confirmation they meet the eligibility criteria for the study. The trained research assistants will be blind to the allocation status to minimize the post-randomization recruitment bias. The recruitment will continue until the planned number of participants is reached. Participants will receive information on the intervention they are assigned to after the baseline collection of data.

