3.2.1.14 Sample size and power calculation

The sample size calculation is based on the following assumptions: two-sided alpha level of 0.05 and power of 0.80. The study group decided that the ability to detect an effect size of 0.5 standard units at the total score at the WHO Organization's questionnaire on the attitudes towards people with psychosocial disabilities as rights-holders between the two groups would be worth finding. The unit of randomization will be the hospital units. The 28 hospitals unit clusters will be randomized with a 1:1 allocation ratio to the intervention or control arm. Based on data from previous cRCT in Ghana [182, 183], we assume a 20% loss to follow-up and ICC=0.05. Based on these assumptions, we calculated that 126 participants would be required in each arm group.

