Since the data are continuous and longitudinal, linear mixed-effects (LME) regression models will be used to estimate average intervention effects while considering the shared variance of repeated measures and the clustered variance. Correlations arising from repeated measures will be accounted for by specifying an autoregressive covariance structure. Each outcome will be analyzed separately using LME. Time, intervention arm, and their interaction will be included in the model as fixed effects, while participants will be evaluated as random effects. Time will be entered as a categorical variable with levels corresponding to post-training and 3 AND 6 months. The effect of the intervention on the outcomes will be captured by the interaction between intervention and time, which will assess the mean difference between the intervention arms (QR e-training vs. control) in changes of outcomes over time within each group. Effect sizes will be reported as mean differences for each time point and intervention arm, with 95% confidence intervals.

(Random intercept with two group-level covariates and interaction).

Level 1:

$$Y_{ij} = b_{0j} + \varepsilon_{ij}$$

Level 2:

$$b_{0j} = \beta_{00} + \beta_{01}w_j + \beta_{02}t_j + \beta_{03}w_jt_j + b_{0j}^*$$

Combined:

$$Y_{ij} = \beta_{00} + \beta_{01}w_j + \beta_{02}t_j + \beta_{03}w_jt_j + b_{0j}^* + \varepsilon_{ij}$$

- Y_{ij} = attitudes
- β_{00} = "average mean" of units mean attitudes

- b_{0j}^* = difference between specific unit mean attitudes and “average mean” of units mean attitudes
- ε_{ij} = difference between individual attitudes and unit mean attitudes
- t_j = time (3 = at 6 months; 2 = at 3 months; 1 = post – training; 0 baseline)
- w_j = (1 = QR training; 0 control)
- β_{02} = regression coefficient for time
- β_{01} = regression coefficient for unit average attitudes when assigned to QR
- β_{03} = regression coefficient for the interaction of time and intervention

3.1.2.4 Secondary analyses.

Secondary outcomes will be the change in practices and experiences related to substitute-decision making and coercion. The change in practices will be evaluated at three months and six months, while the change in experiences will be evaluated both post-intervention and at three months and six months. These changes will be evaluated using the same methodology already described for the main analyses.

References

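### Units are randomised within hospital, but the written-out model has no hospital term: no bias, but some avoidable loss of precision

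*Protocol*

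**What the plan says.** - **Allocation.** Protocol 3.1.1.3 first samples the units: "28 units (12 from Accra, 12 from Pantang, and 4 from Ankaful) will be randomly selected". Then, "within each of the three psychiatric hospitals, units will be randomized to the intervention and control arms using a 1:1 allocation ratio". Hospital is therefore a stratification factor, with 6/6, 6/6 and 2/2 units by arm, or 14 per arm.
- **Model.** Protocol 3.1.2.3: "Time, intervention arm, and their interaction will be included in the model as fixed effects", with participants as random effects. The equation that follows has a unit random intercept, arm, time and their product. Hospital is in neither.
- **Effect measure.** The same section takes the intervention effect from the arm-by-time interaction, with baseline coded as time 0. It also promises mean differences at each time point with 95% confidence intervals.
- **Secondary outcomes.** Section 3.1.2.4 reuses the method, so it inherits the omission.
- **Planning.** Section 3.2.1.14 uses "two-sided alpha level of 0.05 and power of 0.80", "the ability to detect an effect size of 0.5 standard units" on the attitudes total score, "we assume a 20% loss to follow-up and ICC=0.05", and concludes that "126 participants would be required in each arm group". The ICC is not split into hospital and unit parts.
- **Data.** Hospital and unit are recorded at baseline (3.2.1.10, sociodemographic item IX).

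**The concern.** Because the arms are balanced within each hospital, differences between hospitals cannot contribute to the arm difference. If the model has no hospital term, those differences stay in the between-unit variance and enter the standard error all the same. With only 28 clusters, between-unit variance matters for precision, and the gain that stratification should bring is not collected. What is at stake is interval width and power, not validity. How much is lost depends on which contrast is meant, because the protocol uses two: the interaction (a difference in changes) and the arm difference at each visit.

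**Working it through.** **1. The plan's own figure.** Inputs from 3.2.1.14: d = 0.5, two-sided alpha 0.05, ICC 0.05, 20% loss, 14 units per arm. With total variance 1 and m completers per unit, a unit mean has variance V = 0.05 + 0.95/m, and SE = √(2V/14) = √(V/7). Power comes from the noncentral t with 28 − 2 = 26 df.
- m = 6: V = 0.2083, SE = 0.1725, power 0.797, just short.
- m = 7: V = 0.1857, SE = 0.1629, power 0.840.
- 7/0.8 = 8.75, rounded up to 9 per unit; 9 × 14 = 126 per arm. The figure reproduces.

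**2. How much hospital variance leaks into the standard error.** Let σ² be the variance between hospitals. Within an arm of 6, 6 and 2 units, the share of σ² that enters the estimated unit variance when hospital is omitted is [14 − (36 + 36 + 4)/14]/13 = 8.571/13 = 0.659. Hence

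SE with hospital = √(V/7); SE without hospital = √[(V + 0.659σ²)/7].

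**3. Arm difference at one visit**, with 9 × 0.8 = 7.2 completers per unit. The residual part is 0.95/7.2 = 0.1319. Type I error and power come from 40,000 simulated trials per row, analysed on unit means.

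| Assumed hospital variance | V | SE with | SE without | Ratio | Type I error without | Power without / with |
|---|---|---|---|---|---|---|
| 0.025, inside the ICC of 0.05 | 0.1569 | 0.150 | 0.157 | 1.05 | 4.0% | 87.6% / 89.5% |
| 0.05, on top of it | 0.1819 | 0.161 | 0.175 | 1.09 | 3.6% | 80.3% / 84.7% |
| 0.10, on top of it | 0.1819 | 0.161 | 0.188 | 1.17 | 2.9% | 75.5% / 84.3% |

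The losses are 1.9, 4.4 and 8.8 points. A separate simulation with 7 completers per unit gives 84.5% / 86.8%, 76.3% / 81.0% and 71.8% / 80.9%: lower levels, similar gaps.

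**4. Arm-by-time interaction, constant hospital differences.** A hospital level that is the same at every visit drops out of each change from baseline. In a four-visit mixed model with hospital variance from 0 to 0.10, the SEs of the three interaction terms are 0.105, 0.120 and 0.124, identical with and without hospital. Simulated power is about 0.90 and type I error about 0.05 either way.

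**5. Arm-by-time interaction, change differing by hospital.**
- *Unit-level analysis of change*, 7 completers per unit. The SE with hospital is about 0.149, so V = 7 × 0.149² = 0.155. Simulation at a hospital-by-time variance of 0.0125 gives SE 0.153 against 0.149 and power 89.0% against 89.9%. At 0.025 it gives 0.157 against 0.149 and 87.2% against 89.2%. At 0.05 the formula gives √[(0.155 + 0.659 × 0.05)/7] = 0.164, about 10% too large, and the power loss is about 4 points.
- *Mixed model with intercept-type random effects only*, as the protocol writes it (compound symmetry, residual variance 0.45 assumed). The SE is 0.9%, 1.7% and 3.3% too large at 0.0125, 0.025 and 0.05. At 0.05, type I error is 4.1% against 4.9% and power 58% against 60%, for an effect of 0.3.

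**6. Cost of the term if hospitals do not differ.** At 7.2 completers, moving from 26 to 24 df takes power from 0.847 to 0.845.

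**The case against.** The strongest objection is that the plan's effect measure is the interaction, so the single-visit figures concern a different contrast. That stands. A reader might infer that omitting hospital makes the trial's standard errors wrong across the board. The documents do not support this, because constant hospital differences leave the interaction untouched. What keeps the point alive is that 3.1.2.3 also reports mean differences at each time point, and 3.2.1.14 states the target as a between-group difference in total score.

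A reader might also infer that the trial falls below its planned 80% power. The rows that approach or cross that line add hospital variance beyond the stated ICC of 0.05. With half of that ICC between hospitals, single-visit power stays above 80%.

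Nor do the hospitals' differing sizes settle the matter. Appendix 3 gives 823, 486 and 483 staff over 19, 19 and 6 inpatient units, but that says nothing about knowledge or attitude scores.

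It is fair to add that the tests are conservative only if the model carries a suitable unit-level variance. Section 3.1.2.3 conflicts with itself on this: participants are random in the prose, units in the equation. With an assumed unit-by-visit variance of 0.025, type I error is about 8% with or without hospital (8.3% and 7.8% in some order of the two models). That problem matters more for the standard errors, and a hospital term does not cure it.

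Finally, covariates could be called a detail for the analysis plan. Here, however, the protocol writes out the model and lists its fixed effects, and that list does not match its own randomisation.

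**Conclusion.** The point holds in a limited form. The written-out model does not reflect the stratified allocation. The estimate is unbiased, and the omission itself does not raise the false-positive rate. For the interaction there is no loss if hospital differences are constant over time. If change differs by hospital, the standard error is about 1 to 10% too large and about 1 to 4 points of power are lost, at assumed hospital-by-time variances of 0.0125 to 0.05 and depending on how clustering is modelled. For the mean differences at each time point, intervals are too wide and tests conservative whenever hospitals differ: about 2 points of power with half of the ICC between hospitals, and 4 to 9 points only with 0.05 to 0.10 added on top. The documents give no between-hospital variance, so these are ranges under assumptions, not estimates. This is an inexpensive improvement worth making, not a threat to validity.

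**What to change.** Add hospital (three levels) and hospital-by-visit as fixed effects in the primary and secondary models, and state this before the data are unblinded so that the covariate is not chosen afterwards. Hospital alone would not help the interaction; the hospital-by-visit term is what serves it. The cost is one line of text and 2 degrees of freedom per visit, which is under 0.5 points of power if hospitals do not differ. No new data are needed and 126 per arm is unchanged. The conflict over whether participants or units are the random effect must be resolved separately.

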3.1.1.4. Eligibility criteria

Inclusion criteria

Participants must be:

1. **Aged 18 years or older.**
2. **Able to speak English.** English is an official language of Ghana and is used as a lingua franca throughout the country. English is also the most used of the eleven official languages spoken in Ghana [179].
3. **Mental health professionals currently working in the in-patient units of the three psychiatric hospitals** (e.g., psychiatrists, psychologists, nurses, occupational therapists, and social workers).

Exclusion criteria

1. **Persons who participated to the in-person WHO QualityRights trainings held in Ghana** (only a small number of mental health professionals working in the three psychiatric hospitals have participated in the in-person training, so selection bias should not be an issue).
2. **Persons enrolled in the online WHO QualityRights training.** The online version of the QualityRights training is available to Ghanaian stakeholders for free. Persons enrolled in the online training at recruitment will be excluded from the study to avoid contamination (only a small number of mental health professionals working in the three psychiatric hospitals have completed the online training, so selection bias should not be an issue).

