3.1.1.6. Interventions in the study

Intervention arm

Participants assigned to the intervention arm will be enrolled in the QualityRights online training, which aims to increase knowledge about the rights of people with psychosocial disabilities and change negative attitudes towards these persons and their role as rights holders. Furthermore, the training provides mental health professionals with the skills necessary to support people with psychosocial disabilities to advocate for their rights. The QualityRights online training includes five core modules: 1) Human rights; 2) Mental health, disability, and human rights; 3) The right to health and recovery; 4) Legal capacity and the right to decide; 5) Free from coercion, violence, and abuse [see Appendix 2 for further information about the online training topics]. Each module is composed of presentations, videos, interactive exercises, and forum discussions involving all participants. In the forum discussions, particular attention will be given to issues relevant to the Ghanaian context.

The discussions will be moderated by QualityRights trainers selected from a multidisciplinary team, including people with psychosocial disabilities, professionals working in mental health or the disability field, family members, and other local stakeholders.

Control arm

Mental health professionals assigned to the control arm will be enrolled in the WHO novel coronavirus 2019 online training series [see Appendix 4 for further information about the training topics and agenda]. This

trainings series provides a general introduction to COVID-19 and similar respiratory infections and information on what facilities and professionals should be doing to prevent and respond to COVID-19 cases. The training is similar in length to the WHO QualityRights training (12 hours 15 minutes vs. 19 hours) and is intended for health professionals and other stakeholders. To evaluate the integrity of this placebo intervention condition, we will collect information on potential enrollment in the online QualityRights training or other potential interventions at each assessment point.

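### Staff enrolled in the free online QualityRights course are excluded only at recruitment; nothing visible discourages control participants from enrolling later, and Appendix 5 does not record enrolment at six months

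*Protocol*

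**What the plan says.** - **Eligibility (section 3.1.1.4, exclusion 2).** The rule is tied to one moment: "Persons enrolled in the online training at recruitment will be excluded from the study to avoid contamination". The same item says the online course costs Ghanaian stakeholders nothing and that few staff of the three hospitals have completed it. The rule is worded in terms of being enrolled, while its parenthesis speaks of completion.
- **Control arm (section 3.1.1.6).** To check the integrity of the placebo condition, the protocol says "we will collect information on potential enrollment in the online QualityRights training or other potential interventions at each assessment point".
- **Schedule (Appendix 5).** The item on enrolment in the online course is marked at pre-intervention, post-intervention and three months. It has no mark at six months. The item on other interventions has the same gap.
- **Contamination (section 3.2.1.12).** The measures are the cluster design, physical separation of units, a request not to share information with staff of other units, and recording of cross-arm contacts.
- **Blinding (section 3.2.1.11).** Participants are not blinded. They learn their arm after the baseline assessment and are not told the hypotheses.
- **Context (section 2.6).** Of the Ghanaian partners: "they are planning to use the WHO QualityRights online modules to train different stakeholders, including mental health providers". The sentence goes on to say that they want the training evaluated before national scale-up.
- **Analysis (sections 3.1.2.3 and 3.1.2.4).** The analysis is by intention to treat. The effect is read from the arm-by-time interaction at post-training, three and six months. Change in practices is evaluated only at three and six months.

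**The concern.** The protocol recognises that the tested course is openly available and treats this as a contamination risk, but acts on it only at entry. From arm disclosure to the six-month visit, a control participant may take the course at any time. The measures in section 3.2.1.12 concern what one member of staff passes to another, and none of them bears on self-enrolment.

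Under intention to treat, each control participant who takes the course and benefits narrows the difference between arms. Uptake can only accumulate, so any dilution is greatest at three and six months. There it could look like a fading effect, and the practices outcome has no earlier assessment. Enrolment data would help to separate the two explanations, but Appendix 5 leaves them out at six months, the visit where the question is sharpest.

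The exclusion wording has a smaller gap of its own. Read literally, it admits someone who completed the online course earlier and is no longer enrolled.

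**Working it through.** **Inputs from the protocol (section 3.2.1.14)**
- Test and power: "two-sided alpha level of 0.05 and power of 0.80".
- Target: "the ability to detect an effect size of 0.5 standard units at the total score" of the attitudes questionnaire.
- Clusters: "The 28 hospitals unit clusters will be randomized with a 1:1 allocation ratio to the intervention or control arm", so 14 per arm.
- Loss and clustering: "we assume a 20% loss to follow-up and ICC=0.05".
- Result: "126 participants would be required in each arm group".
- No allowance for crossover is stated.

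**Input not in the protocol (assumption)**
- c is the share of controls who have taken the course by the visit analysed. Values from 0% to 20% are used. Each crossover is assumed to gain the full effect, so the intention-to-treat effect is 0.5 × (1 − c) SD.

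**Step 1. Reproduce 126 per arm.** With m completers per unit, the design effect is 1 + (m − 1) × 0.05 and the effective n per arm is 14m divided by it. Using the noncentral t with 2 × (14 − 1) = 26 df and an effect of 0.5 SD:
- m = 6 gives power 0.797, just short.
- m = 7 gives power 0.840, so 7 completers per unit are needed.
- Allowing for 20% loss, 7 / 0.80 = 8.75, rounded up to 9 per unit.
- 9 × 14 = 126, which matches the protocol.

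**Step 2. Precision at the planned size.**
- Completers per unit: 126 × 0.80 / 14 = 7.2.
- Design effect: 1 + 6.2 × 0.05 = 1.31.
- Effective n per arm: 14 × 7.2 / 1.31 = 76.9.
- Standard error of the difference: √(2 / 76.9) = 0.161 SD.

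**Step 3. Power under control uptake.**

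| Control uptake c | Effect (SD) | Power (t, 26 df) | Power (normal approximation) |
|---|---|---|---|
| 0% | 0.500 | 0.847 | 0.873 |
| 5% | 0.475 | 0.809 | 0.838 |
| 10% | 0.450 | 0.766 | 0.797 |
| 20% | 0.400 | 0.666 | 0.699 |

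Power drops below 0.80 just above 6% uptake on the t calculation, and just under 10% on the normal approximation. With 14 × 7.2 = 100.8 control completers, 6% is about 0.06 × 100.8 = 6 people across the 14 control units.

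**Step 4. Compare the monitoring statements.** Section 3.1.1.6 promises enrolment data at every assessment. Appendix 5 lists assessments at pre-intervention, post-intervention, three months and six months, and marks the enrolment item at the first three only. The two cannot both be followed, and the schedule as printed misses enrolment between three and six months.

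**The case against.** Several points on the other side stand.

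- **Entry exclusion as the sole safeguard.** A reader might infer that the protocol has no other protection against contamination. Section 3.2.1.12 does not support that: it lists several measures, and participants are not told the hypotheses. Those measures simply do not reach self-enrolment.
- **A national roll-out reaching controls during the trial.** A reader might infer this from the first half of the sentence in section 2.6. Its second half places national scale-up after the evaluation. What remains is a course that is already free, not a competing programme, so asking the Mental Health Authority to hold back a roll-out would rest on weak ground.
- **Substantial loss of power.** A reader might take 10% uptake or more as the expected case. The protocol's only statement on uptake is that few staff have completed the course, although it is free. At 5% uptake the planned 80% is kept, and partial completion would dilute less than assumed. Past uptake does not, however, bound uptake by staff who have joined a trial and know that they were not given the course.
- **Crossover is foreseen.** Enrolment data are to be collected, and section 1 says that non-adherence should be assessed. How the data enter an analysis may be set out in a statistical analysis plan that is not shown, so that is no fault here. Measuring crossover still does not prevent it, and the six-month gap weakens the measurement.
- **Unseen consent material.** A request to wait could stand in consent pages that were removed from the text. Section 3.2.1.12, which states what participants will be asked, does not include one.
- **Earlier completers.** The parenthesis in exclusion 2 suggests the intent was to keep them out, and any who entered would be expected in both arms. This is a matter of wording.

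**Conclusion.** The point holds as a gap in protection and in recording. Exclusion 2 acts only at entry, the contamination measures do not touch self-enrolment, and the protocol contradicts itself on whether enrolment is recorded at six months. The contradiction is a matter of text and needs no assumption.

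The size of any dilution depends on uptake, which the protocol does not give. On the assumption of full benefit for each crossover, with the protocol's 126 per arm, 14 units per arm, ICC 0.05 and 20% loss, power is about 85%, 81%, 77% and 67% at 0%, 5%, 10% and 20% control uptake. The margin over 80% is used up just above 6%. Under intention to treat the bias is toward the null: the risk is a missed or understated effect, mainly at the later visits, and not a false positive. The protocol does not show that such uptake is likely.

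**What to change.** 1. **Section 3.1.1.4.** Reword exclusion 2 to cover persons *ever enrolled in or completed the online QualityRights training*.
2. **Section 3.2.1.12.** Add a request that participants take no QualityRights course outside the study until their six-month assessment, with access for control staff afterwards. Make the request when the arm is disclosed after baseline. Making it at consent would name the tested course to everyone before baseline.
3. **Appendix 5.** Add the six-month mark for the enrolment item so that it agrees with section 3.1.1.6, and do the same for the other-interventions item. Where platform records are available, check self-report against them.

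The cost is protocol wording, one added item at the six-month visit and, where possible, a records check. The downside is that control staff who agree wait some months for a course they could take now. No extra participants are needed. By comparison, keeping 80% power through recruitment alone, with 14 units per arm, would take 168 per arm at 10% uptake (9 completers per unit; 9 / 0.80 = 11.25, rounded up to 12; 12 × 14) and 210 at 20% (12 completers per unit; 12 / 0.80 = 15; 15 × 14).
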